High resolution photographs from multiple angles will be taken in identical lighting and position with the VISIA CR and with the Fotofinder at 2 weeks, 4 weeks, 8 weeks, and 12 or 16 weeks. Additional real time video telemedicine visits will take place at 6 months and 12 months. In addition, a 72-hour safety phone call will be completed with the subject after each injection session. All visit timing will be based on the last injection session. Oneblinded dermatologist and one unblinded dermatologist will rate the patient's severity of jowling based on the Jawline Rating Scale (JRS) (1) at the 4-week, 8-week, and either 12 or 16-week visits. The patient will also rate their jowling based on the JRS as well as their satisfaction with the procedure.

Name and Intended Use of Devices and Medications

Proprietary name: JUVÉDERM VOLUMA™ XC Common name: non-animal hyaluronic acid Intended use: correction of cheek volume loss

Materials

The devices will be maintained according to the manufacturer's suggested maintenance. The devices will be utilized as packaged with only the needles that were included in the packaging and without manipulating the filler device or contents. No cannulae will be utilized for this study.

If needed for an adverse event, hyaluronidase will be utilized and will be stored according to manufacturers' specification (Hylenex recombinant hyaluronidase human injection, 150 USP units/cc).

Benefit / Risk Analysis

The benefits of participating in this study are to potentially improve moderate to severe facial volume loss leading to an aging appearance, specifically in the jowls.

Commonly reported side effects (SEs) of JUVÉDERM® injectable fillers include, but are not limited to, injection-site erythema or redness, swelling, pain, tenderness, discomfort, firmness, lumps/bumps, bruising, discoloration, and itching. As most of these risks are common to filler injection procedures, the treating physician (TI) will use his/her medical judgment to determine any necessary intervention(s).

Additional risks to undergoing a treatment like this include infection, blindness, stroke, vascular compromise, and scarring. More detailed information regarding the possible Adverse Events (AEs), safety assessments, and investigator protocol in the event of intravascular injection will be noted below.

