- c. There may be discomfort / pain / bruising and complete discussion of side effects potentially resulting from the treatment, including possible stroke, blindness and scarring
- d. Transient edema may occur immediately following the treatment.
- e. Erythema and bruising may occur following treatment and last up two weeks or longer.
- f. A full disclosure and written consent will be provided and signed.
- g. If necessary as deemed by patient and/or physician, a touch up may be performed at the 1-month visit.
- h. Evaluations by phone and/or telemedicine will be performed at 72 hours after treatment, 6 and 12 months.
- I. Patients will complete a safety diary daily via email for 30 days following treatments.

If the patient passes all of the inclusion and exclusion criteria for entry into the study the investigator will obtain signed Informed consent, enroll the patient into the study, and record required data on the appropriate study data form. Pre-treatment photographs will be taken.

Treatment

- 1. Photographs will be taken prior to treatment with the VISIA CR system and Fotofinder and with an iPad. Frontal, 45- and 90-degree angle shots at standard illuminations will be taken.
- 2. Patients will be randomized to 2 groups:

Patient Group 1: JUVÉDERM VOLUMA™ XC 1-2 syringes (each syringe is 1 cc) in will be injected bilaterally into the lateral Jawline/lateral medial or and inferior cheek area (preauricular area) (the latter area will be added if necessary to achieve visual improvement in jowl attenuation). Total syringes used per person will have a range of 1-2.

Patient Group 2: JUVÉDERM VOLUMA™ XC 1-3 syringes (each syringe is 1 cc) will be injected bilaterally into the lateral cheek (zygomatic) area plus JUVÉDERM VOLUMA™ XC 1-2 syringes (each syringe is 1 cc) will be injected into the lateral jawline and inferior cheek area (preauricular area) (the latter area will be added if necessary to achieve visual improvement in jowl attenuation). Total syringes used per person will have a range of 2-5.

Note: Based on preclinical studies and a toxicological risk assessment, subjects will be limited to 20 mL of JUVEDERM VOLUMA™XC per 60 kg (130 lbs) body mass per year. This includes any "Touch-up Volume"

3. During treatment cold air will be directed toward the injection sites to reduce discomfort.

- 4. Any complications will be noted at each visit and the patient will complete a diary via email or text every day.

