Ophthalmologic exams that include Snellen Eye Exam, Ocular Motility Exam, and Confrontational Visual Fields Exam. These exams will be performed prior to any treatment, 30 minutes after treatment, and at all follow up in person visits. Refer to the case report forms (CRFs) for examination procedures.

To further assess vision and oculomotor function, cranial Nerves II, III, IV, and VII will be assessed (left and right sides separately). To assess lower face function, cranial nerves V, VII, IX, X, and XII will be assessed. These exams will be performed prior to any treatment, 30 minutes after treatment, and at all follow up visits. Subjects will also be asked about cranial nerve functionality in their safety diaries. Refer to the case report forms (CRFs) for examination procedures and criteria.

Patient will also have a jaw function assessment at all in person visits. Please refer to the CRF for examination procedures and criteria.

Patients will fill out a daily safety diary to monitor for any adverse events. Patients will be instructed to seek immediate medical attention if any signs of vascular compromise occur (pain in treatment site, excessive redness, purple coloration or blanching (white patches), blisters, and crusts.

Adverse Reactions

AEs will be monitored at every patient visit and through patient safety diaries completed daily for 1 month following treatment. Patients will be followed for a period of 12 months after final treatment.

Adverse Events of Special Interest, including vision changes, will be reported to Allergan and the FDA within 10 days. SAEs will be reported within 24 hours. All other AEs will be reported annually.

More detailed information including the AE report form will be included below.

The following is a list of common anticipated adverse reactions that have been reported with facial injection procedures in the area or at the injection site:

- Bleeding
- Bruising
- Redness
- Swelling
- Lumps/bumps mass or nodule
- Itching
- Discoloration

In rare circumstances, facial fillers have been associated with the following severe adverse events (SAEs):

- Allergic reaction
- Herpes Simplex Virus 1 outbreak
- Giant cell reaction or granuloma formation
- Vision changes (blurred vision, double vision, loss of peripheral vision, partial loss of the visual field)
- Blindness (complete or partial)
- Stroke
- Vascular compromise
- Scarring
- Skin necrosis, ulceration and/ or nerve damage
- Inability to chew or speak normally

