- 10. Incidence of abnormal cranial nerves II, III, IV and VII assessments findings (Safety):

 To further assess vision and oculomotor function, cranial nerves II, III, IV, and VII will be assessed
 (left and right sides separately). To assess lower face function, cranial nerves V, VII, IX, X, and XII will be assessed. These exams will be performed prior to any treatment, 30 minutes after treatment, and at all follow up visits. [Time Frame: up to 18 months]
- 11. Adverse events:

Adverse events will be recorded until 12 months after last treatment. [Time Frame: up to 12 months after last treatment]

Adherence to Protocol

The investigator will review the contents of this protocol. Any alterations to the protocol will be made in writing to the sponsor.

Records and Reports

Data from the pre-treatment evaluation, the treatment procedure, complications, if any, the post-treatment evaluation and all follow up evaluations will be recorded on the clinical data forms prepared for the study.

All records and reports concerning the clinical study will be forwarded to the Sponsor within a reasonable amount of time. The Investigator shall retain copies of all documentation for a period of two years following the date on which the entire clinical investigation is terminated or discontinued.

Confidentiality

This study is confidential. Information made public regarding subjects enrolled in this study will not disclose the name of any individual.

Information made public regarding subjects enrolled in this study will not disclose the name of any individual. All our research records are stored securely in locked cabinets and password protected computers. Only a few people who are closely concerned with the research will be able to view information from participants. Data is coded.

The results of this study will be provided to Allergan, including photographs, but no identifying subject information will be disclosed.

The results of this research study may be presented at scientific or medical meetings or published in scientific journals. Subject identities will not be disclosed in any of these meetings or publications.

A description of this clinical trial will be available on http://www.ClinicalTrials.gov, as required by

U.S. Law. This Web site will not include information that can identify subjects. At most, the Web site will include a summary of the results.

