sp	ots, problems movin		YES	ain in or around your eye, blindness, NO
		any portion of the face? Moderate		
• Cr	rusty or scabby skin a	round the eyelids or any o		e face NO
Ify	es was it Mild	Moderate		

		in in any area?	YES	_ NO	_
	If yes was it Mild	Moderate	Severe		
•	Moderate to Severe He			NO	_
	If yes was it Mild	Moderate	Severe		
•	Fever			_ NO	_
	If yes was it Mild	Moderate	Severe		
•	Difficulty Chewing or Sv	vallowing	YES	NO	_
	If yes was it Mild	Moderate	Severe	.	
•	Moderate to Severe Pa	in in Jaw at Rest	YES	NO	
	If yes was it Mild				
*If	you have answ	ered yes to ar	ny of the abo	ve ques	tions, please c
ie d	office immedia	tely at [name] durin	g busine	ess hours, or D
	at [name]				-
и и к	[name]	do il alter liot	 		
	These questions will any of the following	•	vents that may occ	ur. Please le	et us know if you have
1.	Have you noticed an				NI -
	•	y other symptoms no	ot listed above?		
	If yes, list symptoms				
	If yes, list symptoms If yes was it Mild Have you had any co	Moderate_	Severe since your last diar	y? Yes	 No
2.	If yes, list symptoms If yes was it Mild Have you had any co If yes, please list Have any symptoms	Moderate_ ontinuing symptoms s	Severe since your last diar	y? Yes	No
2.	If yes, list symptoms If yes was it Mild Have you had any co If yes, please list Have any symptoms If yes, please list Any change in medic	Moderate_ ontinuing symptoms s /side effects subside	Severe since your last diar	y? Yes Yes	No
2.	If yes, list symptoms If yes was it Mild Have you had any co If yes, please list Have any symptoms If yes, please list Any change in medic Yes No	Moderate_ ontinuing symptoms s /side effects subside	Severe since your last diar diary?	y? Yes Yes lications sin	No No No ce your last visit or di
2.	If yes, list symptoms If yes was it Mild Have you had any co If yes, please list Have any symptoms If yes, please list Any change in medic Yes No If yes, list medication Have you been diagnorms	Moderate_ontinuing symptoms solutions symptoms solutions subside cations, including over the cations of t	Severe since your last diary? d since last diary? er the counter medical conditions	y? Yes Yes lications sin	No No ce your last visit or di

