 3. 4. 	If yes, list symptoms If yes was it Mild Have you had any co If yes, please list Have any symptoms If yes, please list Any change in medic Yes No If yes, list medication Have you been diagnorms	Moderate_ ontinuing symptoms s /side effects subside cations, including ove	Severe since your last diary? d since last diary? er the counter medical conditions	y? Yes Yes lications sin	No No ce your last visit or di
 3. 4. 	If yes, list symptoms If yes was it Mild Have you had any co If yes, please list Have any symptoms If yes, please list Any change in medic Yes No If yes, list medication Have you been diagr Yes No Have you had any ill	Moderate_ ontinuing symptoms s /side effects subside cations, including ove ns nosed with any new r If yes, please list	Severe since your last diary? d since last diary? er the counter medical conditions	Yes lications sin since your Yes	No ce your last visit or di

· - ·	Worst Pain 6 7 8 9 10 6 8 10			
9. Are you experiencing any of the	ne following today:	V.	NI.	
Bruising Mild	NA sala wata		No	-
■ Redness	Moderate	Severe_		
	Moderate	Severe		
■ Firmness				
If yes was it Mild	Moderate	Severe_		
Lumps/Bumps				
If yes was it Mild	Moderate	Severe_		
Itching				
If yes was it Mild	Moderate	Severe_		
Do you feel comfortable going out in				
f not, why not?				_
any other observations or comment y	ou have?			

Jowl Improvement with Injectable Fillers: Jawline Injections alone vs Jawline and Cheek Injections-Operative Note

Subje	ct#	Date_	Stop Time of Inje	action		
				oluma	-	
on the repres	diagran ented by ction as	n by the injector y the labels belo abbreviated her	indicating the below	labels (A1-D2) tten into the bo	. The amount (co	nted by hand drawing) placed in each area injector and the depth
A1:		_cc SC (circle one	both)			
A2:		_cc SC (circle one	both)			
B1:		cc SC (circle one	both)			
B2:		cc SC (circle one	both)		2 may	1 Comment
C1:	P -	cc SC (circle one	both)	V		
C2:	P -	cc SC (circle one	both)			
D1:	P -	cc SC (circle one	both)			
D2:	P -	_cc SC (circle one	both)			
Signat	ture	[name], N	Date _		_	

Cranial	Nerve	Eva	luations	CRF
---------	-------	-----	----------	------------

Subj	ect Number:	Date:	Visit Type:

Cranial Nerves II-VII; IX, X, XII Evaluation Criteria					
Cranial Nerve	Nerve Name	Function	Test		

ASSESSMENT OF CRANIAL NERVES II-VII; IX, X, XII

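### The legible daily diary prompts for five local reactions but not for swelling, so swelling is likely to be under-recorded relative to the prompted reactions

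*Combined protocol and SAP*

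**What the plan says.** Three places lead the reader to expect swelling:

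- Benefit / Risk Analysis gives the product's commonly reported side effects as "injection-site erythema or redness, swelling, pain, tenderness, discomfort, firmness, lumps/bumps, bruising, discoloration, and itching".
- Pre-Procedure Evaluation, item 3d, has the physician tell the patient: "Transient edema may occur immediately following the treatment".
- Adverse Reactions introduces its bullets with "The following is a list of common anticipated adverse reactions that have been reported with facial injection procedures". There are seven, and swelling is one of them.

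On data collection, Adverse Reactions states: "AEs will be monitored at every patient visit and through patient safety diaries completed daily for 1 month following treatment". Secondary outcome 11 says only: "Adverse events will be recorded until 12 months after last treatment". It does not separate reactions that were asked about from those that were volunteered.

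Diary item 9 begins "Are you experiencing any of the" and its legible labels are bruising, redness, firmness, lumps/bumps and itching, with mild, moderate and severe fields. An earlier open question begins "Have you noticed an" (the text breaks mid-word). It asks about symptoms not already listed and is followed by questions on continuing and subsided symptoms. The diary closes with a free-text line asking for "any other observations or comment".

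**The concern.** A reaction that is asked about by name every day is normally recorded more completely than one the patient must think to mention. If five local reactions are prompted and graded daily while swelling is not, an adverse event table from outcome 11 could show swelling as rarer, milder or shorter than bruising or redness merely because nobody asked. The protocol itself says, under Benefit / Risk Analysis, that the balance of benefit and risk for this new use is not fully known. A consistent profile of local reactions is therefore part of what 16 patients can usefully supply.

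**Working it through.** No stated figure is at issue, so the check compares lists and forms, followed by a labelled illustration.

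**1. Can the form be read well enough?** Item 9 is damaged. Firmness, lumps/bumps and itching are intact; the bruising and redness rows are broken. Five labels survive, and five severe fields survive (two before firmness, three after). Each label can be matched to one severe field with none left over. A garbled fragment beside bruising looks like a duplicate of its moderate field. A lost swelling row is therefore unlikely, but not excluded.

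**2. The seven anticipated reactions against item 9.**

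| Anticipated reaction | Prompted in item 9? |
|---|---|
| Bleeding | No |
| Bruising | Yes |
| Redness | Yes |
| Swelling | No |
| Lumps/bumps | Yes |
| Itching | Yes |
| Discoloration | No |

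Four of seven are prompted and 7 − 4 = 3 are not. Firmness, the fifth prompted reaction, comes from the Benefit / Risk list. Discoloration may be partly covered by an earlier diary question of which only a closing reference to the face survives.

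**3. Is swelling prompted elsewhere?** Not on any readable form. The acute-symptom part of the diary, the Physical and Visual Exam, the TMJ exam and the Pain Assessment Form do not name it, nor does the patient questionnaire as described under Return Visits.

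**4. Timing.** Item 3d expects edema straight after treatment and calls it transient. The first return visit is at 2 weeks ± 3 days, that is, day 14 − 3 = 11 at the earliest. Between treatment day and that visit, Appendix 1 schedules only the 72-hour call. The diary is the only daily record in that interval.

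**5. Exposure.** 16 patients × 30 days = 480 diary days after the first session. If every patient had a touch-up, the total would be 2 × 480 = 960. This counts days without a prompt, not missed events.

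**6. Illustration only.** Expected patients recorded = N × true incidence × capture probability, with N = 16 from the protocol. Incidence and capture are assumptions; the documents give neither.

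| Assumed incidence | True patients | 30% capture | 50% capture | 80% capture | 95% capture (prompted) |
|---|---|---|---|---|---|
| 50% | 8.0 | 2.4 | 4.0 | 6.4 | 7.6 |
| 70% | 11.2 | 3.4 | 5.6 | 9.0 | 10.6 |
| 90% | 14.4 | 4.3 | 7.2 | 11.5 | 13.7 |

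For example, 16 × 0.70 × 0.30 = 3.4 against 16 × 0.70 × 0.95 = 10.6. Under these assumptions swelling would appear at between 0.30 / 0.95 = 32% and 0.80 / 0.95 = 84% of the count of a prompted reaction with the same true incidence.

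**7. Between groups.** Let p1 and p2 be the true incidences in Groups 1 and 2. With the same capture probability c in both, the recorded difference is c × (p2 − p1): smaller in size, same sign. If capture differed by group, the direction would depend on values the documents do not give.

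**The case against.** The strongest objection is that the gap may be an artefact of text extraction. A row of moderate and severe fields without a label lies between redness and firmness, about where the order of the Benefit / Risk list would put swelling. Diary items 6 to 8 are mostly lost. The adverse event report form that Adverse Reactions says is included is not in the text available here. All of this stands as a reason to look at the original first. It does not overturn the reading, because the surviving labels and severe fields match one to one.

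The second objection is that swelling has other routes into the data. The open question is asked daily, has a severity grade and is followed up for persistence. Adverse events are also collected at the 72-hour call, the office visits and the video visits, and there is a physical examination at each office visit. This also stands: a reader might infer that swelling is shut out of the data, and that would be wrong. But all of these routes rely on swelling being volunteered or happening to be noticed, and the visits come late for a transient early reaction.

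Third, no planned analysis compares types of reaction, and neither the primary outcome nor the efficacy comparison is touched. That is correct and limits the importance of the point.

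A reader might also infer a biased comparison between groups, since Group 1 receives 1-2 syringes and Group 2 receives 2-5. The documents do not support this. They state no relation between swelling and volume, and both groups complete the same diary.

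**Conclusion.** The point holds in a limited form. On the legible text, swelling is one of three anticipated reactions without an item 9 prompt, and it is the one that the protocol also raises at consent (as edema). It can be recorded, but only as an unsolicited report. Its incidence, severity and duration in outcome 11 are therefore likely, not certain, to be under-recorded relative to the five prompted reactions. The size cannot be derived from the documents, and the illustrated range of 32% to 84% is only as good as its assumed capture rates. No between-group bias in a known direction is shown.

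The conclusion rests on two assumptions: that the original diary has no swelling line lost in extraction, and that no adverse event form outside the available text prompts for it.

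**What to change.** First check the original diary and the adverse event report form. If swelling is absent:

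1. Add a swelling line to item 9, with yes/no and mild, moderate or severe, in the same layout as the other reactions.
2. Compare the rest of item 9 with the lists in Benefit / Risk Analysis and Adverse Reactions, in particular bleeding, discoloration and tenderness, so that anticipated local reactions are asked about in the same way.
3. State under outcome 11 that solicited and unsolicited reactions will be reported separately.

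The cost is a slightly longer emailed form and possibly a higher recorded rate of mild reactions, which should be noted when the results are read. If any patient has already completed diaries on the existing form, record which version each patient used.
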